##### Washout periods

The periods from the day after visits V1B and V2B, to the dates of visits V1C and V2C respectively will be defined as the two washout periods of this trial.

Data collected at visits V1C and V2C will be considered as end-of-washout values for the first and second treatment periods respectively and will be summarised within the same treatment as the end-of-treatment values of the respective treatment period.

If an EDV occurs 6 or more days after the last IMP intake of the preceding treatment period, the data collected at the EDV will be assigned to the end of the ongoing washout period for statistical analyses.

##### Follow-up period

The follow-up period is a trial period starting with the day after visit V3B/EDV until the trial termination date.

## 4.7 Baseline and Endpoint Values

### Baseline value

The baseline value for a variable is defined as the last non-missing value collected before or during visit VR.

For diary data, the baseline value will be the value standardised as described in Section 5.6.8 over the baseline period.

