6.3.3. Vital signs and weight

Vital signs (systolic and diastolic blood pressure as well as heart rate) will be measured twice: after 5 minutes supine rest and after 2 minutes in standing position (one set of supine and standing vital signs).

At VR, V1C and V2C three sets of supine and standing vital signs will be measured with 15-20 min intervals between the sets.

Weight will be measured in street clothes without shoes.

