8.3.2. Safety

Safety parameters will be analysed as follows:

Vital signs: All vital signs data will be listed by treatment, subject, and visit/time and will be flagged vs. predefined clinical normal range. The mean value of vital sign parameter assessments during a visit will be summarized. Summary statistics will be provided by treatment and visit/time. Shift tables will be provided for vital sign abnormality change from baseline to endpoint within each treatment period.

ECG parameters: All ECG parameters data will be listed by treatment, subject, and visit/time and abnormalities will be flagged vs. predefined clinical normal range. Summary statistics will be provided by treatment and visit/time.

A shift table will be prepared to document QT change and distribution vs. baseline.

C-SSRS: C-SSRS score data will be listed by treatment, subject, and visit/time. Summary statistics will be provided by treatment and visit/time.

QUIP-RS: QUIP-RS score data will be listed by treatment, subject and visit/time. Summary statistics will be provided by treatment and visit/time.

MDS-UPDRS: MDS-UPDRS score data will be listed by treatment, subject and visit/time. Summary statistics for each part of the MDS-UPDRS as well as the total score will be provided by treatment and visit/time.

Clinical laboratory evaluations: All laboratory data will be listed by treatment, subject, and visit/time and abnormalities will be flagged vs. common normal range if considered by investigator as clinically relevant. Summary statistics will be provided by treatment and visit/time. Shift tables will be provided for clinical laboratory variables' change from baseline to endpoint.

Adverse events: All information obtained on adverse events will be displayed by treatment and subject after coding with pertinent MedDRA version. All adverse events and related adverse events will be presented. The number and percentage of subjects with adverse events will be tabulated by body system and preferred term with a breakdown by treatment. An adverse event starting in one period and continuing into the next period is counted only in the onset period. A subject with multiple adverse events within a body system is only counted once towards the total of this body system.

Concomitant medications / Significant non-drug therapies: All concomitant therapies will be coded by WHO version and listed by treatment group and subject.

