### Endpoint value

The endpoint value for a variable is defined as the last non-missing value collected during any end-of-treatment visit (V1B, V2B, or V3B).

For diary data, the endpoint value will be the value standardized as described in Section 5.6.8 over any treatment period corresponding to a given treatment.

**Absolute change from baseline** will be calculated as

$$\text{Absolute Change from Baseline at Visit } X = \text{Value at Visit } X - \text{Baseline Value}$$

**Relative change from baseline (%)** will be calculated as

$$\text{Relative Change from Baseline at Visit } X = \frac{\text{Value at Visit } X - \text{Baseline Value}}{\text{Baseline Value}} \times 100$$

Note: Subjects with a baseline value of '0' will be excluded from the calculation of relative change.

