## 4.8 Treatment Assignment

In summaries and analyses where data is pooled by treatment, assignment to treatments will be performed as follows:

- Data collected up to and including visit VR (baseline) will be assigned to all treatments.
- Data collected at visits V1A-V1C, V2A-V2C, V3A-V3B, will be assigned to the treatment corresponding to the first, second and third treatment period respectively
- Data collected at the EDV visit will be assigned to treatment periods according to the rules in Section 4.6
- Efficacy analyses will be performed according to treatment **as randomised**. Data will be assigned to treatments based on the combination of planned treatment sequence and treatment period.
- Safety analyses will be performed according to treatment **as treated**. Data will be assigned to treatments based on the treatment actually received during the corresponding treatment period.

Other features of or deviations from the rules of treatment assignment are discussed in the relevant sub-sections of Section 5.

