## 5.4 Exposure to IMP and Compliance

### 5.4.1 Exposure to IMP

Exposure data from eCRF includes:

- date of first IMP intake
- date of last IMP intake
- date of IMP dispensed
- number of capsules dispensed (modafinil and flecainide)
- date of IMP returned
- number of capsules returned (modafinil and flecainide)

Exposure data from the subject treatment diaries includes:

- date
- number of capsules taken (modafinil and flecainide)

The **date of first IMP intake** is the intake of the first morning dose as recorded in the eCRF. If the date of first intake as recorded in the eCRF is missing, the first IMP intake recorded in the subjects' diaries will be used.

The **date of last IMP intake** is the date of last IMP intake recorded at trial termination page. If the date of last intake of the last evaluated dose is missing, the last IMP intake recorded in the subject diaries will be used.

The treatment period duration will be calculated in days as follows:

$$\text{treatment period duration (days)} = \text{end-of-treatment visit date} - \text{baseline visit date}$$

For the purposes of treatment period duration calculation, visit VR as well as end-of-washout visits V1C and V2C are considered as baseline visits.

Treatment duration based on IMP exposure data will be calculated for each treatment period as:

$$\text{treatment duration (days)} = \text{last IMP intake date} - \text{first IMP intake date} + 1$$

within the respective treatment period. The overall treatment and treatment period durations will be calculated as the sum of corresponding individual durations.

The following will be provided:

Table 15.1.10.1.1.T Treatment Duration (days) – Safety

Table 15.1.10.1.2.T Treatment Duration (days) – Full Analysis

Table 15.1.10.1.3.T Treatment Duration (days) – Per Protocol

The default summary statistics of treatment period duration and treatment duration will be presented by period and overall.

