#### Table 15.2.5.3.T Shift Table of Vital Signs Abnormalities – Safety

Shift tables showing changes in the number and frequency of subjects with respect to the normal range between baseline and endpoint will be provided. Subjects with missing data will be presented as part of a “missing” category.

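### The protocol asks for vital-sign shifts within each period, but the SAP starts every shift at VR and does not declare the difference

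*SAP*

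**What the plan says.** Protocol section 8.3.2 on vital signs: "Shift tables will be provided for vital sign abnormality change from baseline to endpoint within each treatment period". The same section asks for laboratory shifts from baseline to endpoint without the period qualifier. For ECG it says only: "A shift table will be prepared to document QT change and distribution vs. baseline".

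Protocol section 6.3.3: "At VR, V1C and V2C three sets of supine and standing vital signs will be measured with 15-20 min intervals between the sets". The end-of-treatment visits have one set. No laboratory sample is taken at V1C or V2C.

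SAP section 4.7: "The baseline value for a variable is defined as the last non-missing value collected before or during visit VR". SAP section 4.8 adds: "Data collected up to and including visit VR (baseline) will be assigned to all treatments". SAP section 5.5.3 (vital signs) defines no baseline of its own, and for Table 15.2.5.3.T it states: "Shift tables showing changes in the number and frequency of subjects with respect to the normal range between baseline and endpoint will be provided".

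SAP section 4.6 files V1C and V2C readings under the preceding treatment, as end-of-washout values. SAP section 5.4.1 does say that "visit VR as well as end-of-washout visits V1C and V2C are considered as baseline visits", but only for calculating the length of a treatment period. SAP section 7 lists one change from the protocol, to the Per Protocol set.

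**The concern.** Safety is the primary objective, and in a crossover the shift table should show what happened on each treatment. With VR as the only starting point, a period II or III shift spans one or two earlier treatment periods and their washouts. Two errors of attribution can follow.

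- A subject normal at VR who becomes abnormal on active drug, and is still abnormal when the next period starts, is shown as normal-to-abnormal a second time, under a later treatment that may be placebo.
- A subject abnormal at VR, normal at V1C or V2C, and abnormal again at the end of that period is shown as abnormal at both ends. The change during the period disappears. This needs no carry-over.

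The readings that would separate these cases are already collected, but the SAP never uses them as the start of the period that follows.

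**Working it through.** No figure in the plan bears directly on this point. The stated 82% power reproduces (paired t-test, n = 54, effect size 0.40, noncentrality 0.40 × √54 = 2.94, power 82.3%) but is not used below.

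**1. The wording side by side.** In Protocol section 8.3.2 the period qualifier is attached to the vital-sign shifts and not to the laboratory shifts. Vital signs are measured at V1C and V2C; laboratory values are not. Three sets are taken at exactly the visits that precede dosing. The amendment log attributes both the three sets and the revised vital-sign analysis text to an FDA request. Together these favour a baseline for each period.

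**2. Who is exposed.** Sequences ABC, BCA, CAB, ACB, CBA, BAC; 10 subjects each if 60 are randomised equally.
- Placebo in period I: ABC, ACB. Period II: CAB, BAC. Period III: BCA, CBA.
- Placebo after at least one active period: 4 of 6 sequences = 40 of 60 subjects. After both active doses: 20 of 60.
- Period II and III subject-periods: 120. Period II of ABC and ACB (20) follows placebo only, so 100 follow active treatment.

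**3. Residual drug.** Fraction left = 2^(−hours / half-life), with the half-lives in Protocol Table 1.
- Modafinil, 15 h, 7 days: 2^(−168/15) = 0.04%. At 6 days: 2^(−144/15) = 0.13%.
- Flecainide, 13 h (mean; the protocol calls the range wide), 7 days: 2^(−168/13) = 0.01%.

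Double counting therefore needs an abnormality that outlasts the drug itself.

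**4. Illustration of size.** Assumptions, not document figures: each active period makes an unaffected subject abnormal with probability p; an abnormality lasts to the start of the next period with probability r; placebo causes none. With s the probability of being abnormal at the start of a period and e at its end, e = s + (1 − s)p on active drug, e = s on placebo, and the next s = r × e. A VR-based shift has probability e and a period-based shift e − s; both are averaged over the six sequences.

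By hand for p = 0.10, r = 1:
- Placebo, VR-based: (0 + 0.10 + 0.19)/3 = 9.7%.
- Dose C, VR-based: (3 × 0.10 + 3 × 0.19)/6 = 14.5%. Difference 4.8 points.
- Dose C, period-based: (3 × 0.10 + 3 × 0.09)/6 = 9.5%; placebo 0. Difference 9.5 points.

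| r (p = 10%) | Placebo shifts, VR | C − placebo, VR | C − placebo, period |
|---|---|---|---|
| 0 | 0% | 10.0 | 10.0 |
| 0.25 | 1.9% | 9.0 | 9.9 |
| 0.5 | 4.1% | 7.8 | 9.8 |
| 1 | 9.7% | 4.8 | 9.5 |

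At r = 1 the difference is 2.5 against 4.9 points for p = 5%, and 9.3 against 18.0 for p = 20%.

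The ceiling can also be seen by counting. C precedes placebo in BCA, CAB and CBA, 3 of 6 sequences. If all of k shifts first seen on C persisted, about k/2 would reappear under placebo, and the difference would fall from k to k/2.

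**The case against.** The best defence is that the protocol itself calls VR the baseline visit, labels V1C and V2C as end of washout in the flow chart, and in section 6.3.6 equates baseline with VR. The vital-sign sentence could then mean VR to the endpoint reached in each period, which is what the SAP does. No passage says that the three sets serve as period baselines. This stands as far as the wording goes: it is not conclusive. It does not explain why the qualifier is given for vital signs and left out for laboratory values.

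A second defence is that persistence is already visible. Table 15.2.5.1.T gives change from baseline at each visit, including V1C and V2C under the preceding treatment, and there are abnormality counts by visit and individual listings. That is true, but none of the planned tables shows a shift within a period.

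A third is that period baselines have their own faults. They add measurement noise and any carry-over, and they hide a persistent effect: a subject still abnormal at V1C shows no shift in period II. For continuous change in complete cases, a common VR baseline cancels from within-subject treatment differences. All of this stands, and it is the reason to show both tables rather than replace one with the other.

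**Conclusion.** The point holds for vital signs. On the more natural reading of Protocol section 8.3.2, the SAP departs from the protocol without declaring it; on the other reading, the SAP should still state its choice. The 40 of 60 are subjects whose placebo shift could be affected, not subjects who are affected. The actual effect is unknown and may be nil. It rests on a persistence rate that the documents do not give, and p and r above are assumptions.

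A reader might infer more, and the documents do not support it:
- **That persistent changes will be counted again on placebo, halving the difference.** Halving needs every shift to outlast the washout; in CBA it must outlast two washouts and an intervening active period. At r = 0 the two baselines give the same answer.
- **That the ECG shift table breaks the protocol in the same way.** For ECG the protocol asks for QT against baseline and mentions no period, so a VR baseline complies.
- **That every later shift starts before an earlier active treatment.** Period II of ABC and ACB follows placebo only.
- **That SAP section 5.4.1 concedes V1C and V2C as analysis baselines.** It covers period length only.
- **That a formal safety test is biased.** The safety analysis is descriptive.

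**What to change.** - Build Table 15.2.5.3.T with VR, V1C and V2C as the baselines for periods I, II and III, and label the last two as post-randomisation values.
- Keep the VR-based shift table beside it, so that effects lasting beyond the washout stay visible.
- In Table 15.2.5.1.T, show change from period baseline next to change from VR.
- Leave laboratory shifts on VR, since no sample exists at V1C or V2C.
- A supplementary period-baseline display for ECG may be offered as an option; ECGs are recorded at V1C and V2C.
- If the sponsor prefers VR alone for vital signs, state and justify that in SAP section 7.

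The cost is one extra baseline flag, one extra table and some SAP wording; no new data are needed. The downside is that period II and III baselines can carry residual effects of earlier treatment, which is why the VR-based table has to stay.

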### Endpoint value

The endpoint value for a variable is defined as the last non-missing value collected during any end-of-treatment visit (V1B, V2B, or V3B).

For diary data, the endpoint value will be the value standardized as described in Section 5.6.8 over any treatment period corresponding to a given treatment.

**Absolute change from baseline** will be calculated as

$$\text{Absolute Change from Baseline at Visit } X = \text{Value at Visit } X - \text{Baseline Value}$$

**Relative change from baseline (%)** will be calculated as

$$\text{Relative Change from Baseline at Visit } X = \frac{\text{Value at Visit } X - \text{Baseline Value}}{\text{Baseline Value}} \times 100$$

Note: Subjects with a baseline value of '0' will be excluded from the calculation of relative change.

## 4.8 Treatment Assignment

In summaries and analyses where data is pooled by treatment, assignment to treatments will be performed as follows:

- Data collected up to and including visit VR (baseline) will be assigned to all treatments.
- Data collected at visits V1A-V1C, V2A-V2C, V3A-V3B, will be assigned to the treatment corresponding to the first, second and third treatment period respectively
- Data collected at the EDV visit will be assigned to treatment periods according to the rules in Section 4.6
- Efficacy analyses will be performed according to treatment **as randomised**. Data will be assigned to treatments based on the combination of planned treatment sequence and treatment period.
- Safety analyses will be performed according to treatment **as treated**. Data will be assigned to treatments based on the treatment actually received during the corresponding treatment period.

Other features of or deviations from the rules of treatment assignment are discussed in the relevant sub-sections of Section 5.

## 4.9 Coding Systems and Conventions

### 4.9.1 Coding of adverse events and medical history

Adverse event and medical history investigator terms are assigned to a lowest level term (LLT) and a preferred term (PT) and will be classified by high level term (HLT), high level group term (HLGT) and system organ class (SOC) according to the Medical Dictionary for Regulatory Activities (MedDRA), Version 21.0 [2].

### 4.9.2 Coding of medications

Medications are classified according to active drug substance using the World Health Organization-Drug Dictionary Enhanced (WHO-DDE), 2018 March version [3]. The WHO drug code has 11 digits. The generic name is defined by the first 6 of the 11 digits. In addition, the Anatomical Therapeutic Chemical (ATC) classes are assigned to the drug code. In this trial, ATC codes are defined to the 4th level.

### 4.10 Handling of Missing Data

Data imputation methods will not be used in the analysis of efficacy or safety data. Efficacy data will be assumed to be missing at random (MAR), and likelihood-based estimation methods robust to this form of missingness will be used in efficacy analysis. Other details of handling of missing data, where applicable, are discussed in the relevant sub-sections of Section 5 (*STATISTICAL ANALYSIS: DEFINITIONS, DERIVATIONS, CALCULATIONS AND METHODOLOGY*).

## 5. STATISTICAL ANALYSIS: DEFINITIONS, DERIVATIONS, CALCULATIONS AND METHODOLOGY

### 5.1 Subjects Disposition

#### 5.1.1 Disposition and Withdrawals

The following disposition data will be collected:

- date of informed consent
- date of trial termination
- did the subject complete the trial as scheduled (yes, no)
- reason for premature trial termination (at their own request (specified), investigator's opinion, major protocol deviations, treatment incompliance, prohibited concomitant therapy, adverse event, at the specific request of the sponsor, other (specified))

**Screening failures** will be all subjects discontinuing the trial due to any reason prior to randomisation at visit VR.

**Withdrawals** will be all subjects randomised at visit VR who do not complete the trial (visits V1A-V3B) as scheduled.

The following tables and listings will be presented:

##### Table 15.1.1.1.S Analysis Sets – Enrolled

##### Table 15.1.1.2.T Analysis Sets – Enrolled

Number and percentage of subjects included into the enrolled, randomised, safety, full analysis, per protocol, and PK analysis sets will be provided. Percentage will be based on the number of subjects in the enrolled set.

##### Table 15.1.1.3 Reasons for Exclusions from Analysis Sets – Enrolled

Number and percentage of subjects excluded from the randomised, safety, full analysis, per protocol, and PK analysis sets will be provided. Percentage will be based on the number of subjects in the enrolled set. The reasons of exclusion from the analysis sets will be incorporated into the table.

##### Table 15.1.2 Screening Failures – Enrolled

Counts and percentages of subjects who discontinued the trial prior to randomisation at visit VR will be summarised by reasons associated with the discontinuation. Percentage will be based on the number of subjects in the enrolled set.

##### Table 15.1.3.1.S Subject Disposition – Randomised

##### Table 15.1.3.2.S Subject Disposition – Safety

Counts and percentages of subjects who completed the treatment phase as scheduled, drop-outs during the treatment phase will be summarised separately in each period and overall. Reasons associated with the termination will be included. Percentage will be based on the number of subjects in the safety set.

##### Table 15.1.4.1 Number of Subjects by Country and Site – Enrolled

##### Table 15.1.4.2 Number of Subjects by Country and Site – Randomised

##### Table 15.1.4.3 Number of Subjects by Country and Site – Safety

Counts and percentages of subjects will be presented by site. Percentage will be based on the number of subjects in the safety set.

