Secondary objectives:

- To quantify the efficacy of THN102 versus placebo in improving sleepiness.
- To quantify the efficacy of THN102 versus placebo in improving
 - attention, vigilance
 - cognition
- To determine the dose response profile of THN102 versus placebo on efficacy parameters.
- To determine the plasma levels of modafinil and flecainide at steady state.

Methods / trial design:

This is a prospective, double-blind, randomised, controlled trial using a complete 3-way cross-over design. Subjects will attend seven on-site visits and five phone call visits.

The seven trial periods are depicted below:

Screening	Treatment I	Washout I*	Treatment II	Washout II*	Treatment III	Follow-Up
1-2 weeks	2 weeks	1(2) weeks	2 weeks	1(2) weeks	2 weeks	1 week
No treatment	A, B, or C	No treatment	A, B, or C	No treatment	A, B, or C	No treatment

(Dose A = placebo; Dose B = THN102 200 mg/2 mg; Dose C = THN102 200 mg/18 mg.)

* Washout periods can be extended to up to 2 weeks, if this is more convenient for the subject.

At visit VR (baseline visit) the subjects will be equally randomised (1:1:1:1:1:1) double-blind to a treatment sequence containing three treatment periods (shown below).

Sequence	Treatment period I	Treatment period II	Treatment period III
1	Dose A	Dose B	Dose C
2	Dose B	Dose C	Dose A
3	Dose C	Dose A	Dose B
4	Dose A	Dose C	Dose B
5	Dose C	Dose B	Dose A
6	Dose B	Dose A	Dose C

The duration of each treatment period is 2 weeks, with a 1-week washout in between (to avoid carry-over effects) and a 1-week follow-up period after the last treatment period. Washout periods can be extended up to two weeks. THN102 will be administered orally once daily.

Number of subjects (planned): Enrolled and screened: 72, randomised and evaluable (safety): 60, evaluable (efficacy): 54.

Indication: Excessive daytime sleepiness associated with Parkinson's disease.

Inclusion criteria:

1. Subjects with a diagnosis of idiopathic Parkinson's disease as defined by the Movement Disorders Society (MDS).
2. Subjects with Hoehn and Yahr scale score ≤ 4 .
3. Males or females, aged between 18 and 80 years.
4. Body mass index $> 18 \text{ kg/m}^2$ and $< 35 \text{ kg/m}^2$.
5. Subjects should have a complaint of daytime sleepiness impacting their quality of life and/or daytime functioning (e.g. falling asleep while reading or watching TV, while eating or talking with other people).
6. Epworth Sleepiness Scale (ESS) score ≥ 14 .

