4. TRIAL POPULATION

4.1. Number of Subjects

A total of 60 Parkinson's disease subjects with excessive daytime sleepiness will be randomised. Recruitment will be competitive. Dropouts will not be replaced. The target figure is 54 subjects completing the trial as per protocol. To be eligible for inclusion into this trial, each subject must fulfill the following inclusion criteria and none of the exclusion criteria at visit VS1. For the sample size calculation refer to Section 8.5.

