## 3. ANALYSIS SETS AND SUBGROUPS

### 3.1 Analysis sets

The **Enrolled Set (ES)** includes all subjects who have signed the informed consent form.

The **Randomised Set (RS)** includes all subjects randomised at visit VR.

The **Safety Set (SS)** includes all subjects with at least one IMP administration.

The **Full Analysis Set** (FAS) includes all randomised subjects with an evaluable ESS score at the end of at least one treatment period. Evaluability of treatment periods is described in Section 5.6. The efficacy analyses will be conducted on the FAS.

The **Per Protocol** (PP) set includes all subjects in the FAS who have at least one treatment period without a major protocol deviation. Major and minor violations are defined in Sections 5.1.2 and 5.6. The main secondary endpoints (ESS, PVT and cognition) will be analysed with the PP set to demonstrate robustness of the primary analysis.

The **PK analysis set** will include all subjects who have received treatment as per protocol (even if the trial was not completed) and who present no major protocol deviations with an impact on PK.

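### SAP 5.1.1 uses the safety set as percentage base for tables of enrolled and randomised subjects, so the enrolled site percentages would sum to 120% at the planned numbers

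*SAP*

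**What the plan says.** SAP 3.1 defines three sets. The enrolled set "includes all subjects who have signed the informed consent form"; the randomised set is everyone randomised at visit VR; the safety set requires at least one IMP administration.

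SAP 5.1.1 then plans tables on these sets. One sentence covers Tables 15.1.4.1 (Enrolled), 15.1.4.2 (Randomised) and 15.1.4.3 (Safety): "Counts and percentages of subjects will be presented by site. Percentage will be based on the number of subjects in the safety set". The first of the three is titled "Table 15.1.4.1 Number of Subjects by Country and Site – Enrolled".

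The disposition pair, 15.1.3.1.S and 15.1.3.2.S, is handled the same way: "Reasons associated with the termination will be included. Percentage will be based on the number of subjects in the safety set". The first of that pair is titled "Table 15.1.3.1.S Subject Disposition – Randomised".

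The protocol synopsis gives the planned counts: "Enrolled and screened: 72, randomised and evaluable (safety): 60, evaluable (efficacy): 54". Protocol 4.1 adds: "The target figure is 54 subjects completing the trial as per protocol".

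Other tables in the SAP follow a different rule. The enrolled tables 15.1.1.1.S to 15.1.1.3 and 15.1.2 use the enrolled set as base. Where one sentence serves tables on several sets, as for major protocol deviations (15.1.6.1.S and 15.1.6.2.S) and demographics (15.1.7.1.x), the base is the set belonging to each table.

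**The concern.** A percentage of subjects should have a denominator that contains everyone who can appear in the numerator. In Table 15.1.4.1 this fails by design: screening failures are enrolled but never dosed, so they add to the site counts and not to the base. A site with screening failures only would show a positive share of a set that contains none of its subjects.

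In Tables 15.1.3.1.S and 15.1.4.2 it can fail. SAP 5.1.1 counts as a withdrawal any subject randomised at VR who does not complete, dosed or not. Protocol 5.1.3 places the first IMP intake on the day after VR, and section 5.4 says the subject takes it at home, so a subject can be randomised and never dosed. Such a subject would be counted among the withdrawals but left out of the base.

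What is at stake is the accuracy of the descriptive disposition and site tables in the trial report, and a visible inconsistency when percentages sum to more than 100.

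**Working it through.** The documents state no percentage for these tables, so there is no printed figure to reproduce. The check takes the planned counts and follows the SAP's rule as written.

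Inputs:
- Enrolled, E = 72 (protocol synopsis).
- Randomised, R = 60, and safety set, S = 60 (protocol synopsis, one figure for both).
- Completers, C = 54 (protocol 4.1), so withdrawals W = 60 − 54 = 6.
- Randomised but never dosed, u: not given in the documents. It is varied here as an assumption, with S = 60 − u. The undosed are counted among the 6 withdrawals, so u can run from 0 to 6.

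Formulas under the SAP's rule:
- Table 15.1.4.1, sum over sites: E/S.
- Table 15.1.4.2, sum over sites: R/S.
- Table 15.1.3.1.S: completers C/S, withdrawals W/S, sum (C + W)/S = R/S.

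| u (assumed) | S | Enrolled sites, 72/S | Randomised total, 60/S | Completers, 54/S | Withdrawals, 6/S |
|---|---|---|---|---|---|
| 0 (planned) | 60 | 120.0% | 100.0% | 90.0% | 10.0% |
| 1 | 59 | 122.0% | 101.7% | 91.5% | 10.2% |
| 2 | 58 | 124.1% | 103.4% | 93.1% | 10.3% |
| 6 | 54 | 133.3% | 111.1% | 100.0% | 11.1% |

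For a single site with, say, 6 enrolled subjects (an illustrative number), the enrolled table would show 6/60 = 10.0% instead of 6/72 = 8.3% at the planned counts.

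With each table divided by its own set, the results no longer depend on u: 72/72 = 100% for the enrolled sites, 60/60 = 100% for the randomised sites, and 54/60 = 90.0% plus 6/60 = 10.0% for the randomised disposition table.

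**The case against.** The strongest reply is that this is a wording slip in descriptive tables, and largely harmless. At the planned numbers the randomised and safety sets are the same size, so the randomised tables are right as they stand. Raw counts appear beside the percentages, SAP 4.1 requires the denominator to be named in a footnote, and attrition can also be read from the disposition listings and flow charts. The table shells, a separate appendix not available for this review, may already carry the right base.

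Most of this stands, and it limits the point. It does not remove it. The footnote would only disclose the wrong base. Shells with a different base would contradict the SAP text and need reconciling with it. Table 15.1.4.1 is wrong even at the planned numbers.

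Several stronger readings are tempting, and the documents do not support them:
- A reader might infer that completion and withdrawal rates of randomised subjects are overstated as planned. They are not: 54/60 and 6/60 are the same under either base unless a randomised subject goes undosed, and no document says that this happened or is expected.
- A reader might think a disposition table of enrolled subjects is affected. The two tables under that sentence are on the randomised and safety sets; the only enrolled table affected is the site table.
- A reader might compute that a sequence of 10 subjects with one undosed sums to 10/9 = 111.1%. That needs a sequence-specific safety count as base, which the SAP does not state. Read literally, the column would be 10/59 = 16.9%. (The 111.1% in the last row of the table above is a different calculation, 60/54.)
- A reader might link the point to the missing-at-random assumption in SAP 4.10. That assumption does not rest on how a table percentage is based. Undosed subjects do not enter the efficacy analysis either: the full analysis set needs an evaluable ESS score at the end of a treatment period, and SAP 5.6 requires at least 7 days of IMP for a period to be evaluable.
- Nor do the documents say that the site table will have a total row. The statement is that the site percentages sum to 120%, whether or not the sum is printed.

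**Conclusion.** The point holds as a minor error in a stated rule. For Table 15.1.4.1 the base is wrong as written, and the site percentages sum to exactly 120.0% at the planned 72 enrolled and 60 dosed. The sum would be higher if fewer than 60 were dosed with enrolment at 72. For Tables 15.1.3.1.S and 15.1.4.2 the error is conditional: nothing changes at the planned numbers, and each percentage is inflated by the factor randomised/safety if at least one randomised subject takes no IMP. With one such subject, 54 completers and 6 withdrawals, the disposition figures become 91.5% + 10.2% = 101.7% instead of 90.0% + 10.0%.

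The results rest on the planned counts, on IMP going only to randomised subjects, and, for the conditional part, on an assumed number of undosed subjects. The effect is confined to descriptive reporting. No model, test, estimate or safety conclusion uses these percentages.

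**What to change.** In SAP 5.1.1, replace the sentence on the percentage base in two places: under Tables 15.1.3.1.S and 15.1.3.2.S, and under Tables 15.1.4.1 to 15.1.4.3. Name the analysis set of the respective table as the base, in the wording already used in SAP 5.1.2 for Tables 15.1.6.1.S and 15.1.6.2.S. Check that the table shells and footnotes say the same.

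The cost is one sentence in two places and the matching footnotes. No data, derivation or analysis changes.
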